## APPROACH:

**Overview:** The current *pilot* project seeks to determine the safety, feasibility, and impact of preoperative RST program in 25 CS patients who are at high risk for developing post-surgical dysphagia. Thus, this represents a 'proof of concept' study to support subsequent larger-scale clinical trials. Briefly, *Aim 1* will examine the feasibility and safety of the RST program by monitoring treatment adherence, telehealth/in-person session attendance, and closely monitoring adverse events related to RST. *Aim 2* will determine the physiologic impact of the RST program by comparing measurements of forced vital capacity (FVC), MEP, MIP, voluntary cough peak expiratory flow (PEF), and cough spirometry metrics as well as functional measures of dyspnea and (LCADL, Bamboo passage), before versus after RST (i.e., research exam 1 vs. research exam 2, Fig 3). Additionally, a FEES will be performed to index baseline swallowing and to provide secondary treatment outcomes indexed by the validated penetration-aspiration scale (PAS), dynamic imaging grade of swallowing toxicity (DIGEST), the New Zealand secretion scale (NZSS), and the Yale pharyngeal residue severity rating scale (YRS). Completion of Aims 1 and 2 will occur within one month prior to surgery (Fig. 3). *Aim 3* will involve monitoring and collection of health-related outcomes during the postoperative recovery phase and postoperative pulmonary function testing and FEES following extubation. This study timeline is depicted in Figure 3.

[figure not shown]

Fig. 3: Study Timeline.

**Design:** This study represents a *longitudinal pilot cohort study* intended to collect preliminary data regarding the safety and feasibility of a preoperative intervention program, to inform larger comparative studies that will utilize a between groups comparison. Similar study designs have been implemented in other pilot treatment studies in speech-language pathology. While study designs involving group comparisons were considered for this project, the current design was chosen to ensure feasibility and a tightly conducted pilot or proof of concept study to allow detailed and rigorous outcomes and analyses. Further, consideration was given to the nature, scope, budget, and timeline of this grant mechanism intended for new investigators, and it was determined that a smaller, feasible study was most appropriate.

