### Exclusion Criteria:

1. Individuals under the age of 18 or over the age of 90.
2. Pregnant women.
3. Positive for COVID-19 or symptoms of COVID-19.
4. No access to a computer, tablet, or electronic device &/ a stable internet connection for telehealth sessions.
5. Unwilling to undergo testing procedures and/or complete the exercise training program.

**Recruitment:** [name] is a faculty member of the Department of Surgery, Division of Cardiovascular Surgery, and therefore has close ties with this patient population and clinical setting. Further, the ARC Lab has a strong history of successful collaborations with the cardiothoracic surgeons at the UF Heart and Vascular hospital (Drs. [name], [name], [name], [name]) who see patients in this preoperative clinic. Participants will be recruited from the preoperative clinic visit. Drs. [name] and [name] will identify eligible participants who meet inclusion criteria from clinic schedules and will approach identified individuals who will be informed of their potential eligibility to participate and asked if they would like to learn about this study. If they express interest, an approved study team member listed on this protocol will verbally detail the aims of the study, specific requirements for inclusion, and answer any questions from patients and caregivers. They will also be provided with a copy of the informed consent form to read over. Those who wish to be enrolled will sign an informed consent form, will be provided a copy of the signed informed consent form, assigned a subject identifier, and an appointment will be scheduled for their Research Evaluation 1.

**Research Evaluations:** CS patients will undergo three separate research examinations during this study. Before commencing the RST program, an initial research examination (pulmonary function testing, functional speech/dyspnea measures) will be completed. After completing RST and before undergoing surgery, a second research examination (pulmonary function testing, FEES, functional speech/dyspnea measures) will be completed. Finally, postoperatively, a third research examination (FEES) will be completed. The methods for the research examinations are outlined in detail below.

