**Research Evaluation 1:** As previously described, CS patients will undergo evaluations during the preoperative phase immediately before and after the RST program. Research evaluations will take approximately 30-45 minutes to complete. During these evaluations, the following procedures and outcomes will be collected:

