#### **Research Evaluation 2:**

After completing the RST program and prior to surgery, CS patients will undergo PFTs, read the bamboo passage, and complete the LCADL as they did during Research Evaluation 1. Additionally, they will undergo a standardized Fiberoptic Endoscopic Evaluation of Swallowing (FEES). The second research evaluation will take approximately 45 minutes to complete.

Fiberoptic Endoscopic Evaluation of Swallowing (FEES): CS patients will undergo a FEES exam in a dedicated room (UB 1707, UB 1739) in the preoperative clinic or the ARC lab before and after the RST program using an Olympus flexible video HD Rhino Laryngoscope (ENF-V3) connected to a portable video processor and light source (Olympus CV170). To ensure patient comfort, a water-soluble lubricant (Aplicare sterile lubricating jelly 82-280) and, per participant preference, a topical numbing-agent (i.e., lidocaine hydrochloride jelly USP, 2%) will be applied to the nares, and the laryngoscope will be passed trans-nasally through the nasopharynx and hypopharynx until an optimal position is obtained. The topical numbing agent will be used per participant preference and pending physician authorization.

During laryngoscope advancement, the participant may be asked to hum or say “eeeeee” to help visualize anatomy and placement of the laryngoscope. A standardized FEES protocol will be used that includes a combination of voicing and swallowing tasks. Once optimal scope positioning is confirmed, the participant will be asked to perform a series of voicing tasks to allow assessment of laryngeal and vocal fold movement that include: 1) sustained vowel “ah” 2) vowel/sniff alternating task; 3) cheek puff task; 4) breath hold task; and 5) a pitch glide of the vowel “e”. CS patients will be given 5mL Gatorade x2, 10mL Gatorade x2, comfortable cup sip x2, teaspoon pudding x2, cracker x2, and M&Ms x3. A liquid that is colored needs to be used so that it may be visualized during swallowing. Gatorade will be the typical option but if a participant has dietary restrictions or a dislike for Gatorade other options will include grape juice or milk. To ensure patient safety, swallowing trials will be discontinued after two episodes of gross aspiration or if a patient is unable to clear >70% of the bolus. At the completion of the swallowing trials, the laryngoscope will be carefully removed.

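### The plan contradicts itself on when FEES is done, and on either reading the Aim 3 regression of swallowing across timepoints cannot show that RST improved postoperative swallowing

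*Combined protocol and SAP*

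**What the plan says.** **Text placing FEES only after training.** The Research Evaluations paragraph (after Recruitment) lists three exams. Before RST, "an initial research examination (pulmonary function testing, functional speech/dyspnea measures) will be completed". After RST and before surgery, "a second research examination (pulmonary function testing, FEES, functional speech/dyspnea measures) will be completed". Then: "Finally, postoperatively, a third research examination (FEES) will be completed".

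The Research Evaluation 1 section says "During these evaluations, the following procedures and outcomes will be collected" and goes on to describe pulmonary function, cough, dyspnea and speech measures, with no FEES. Research Evaluation 2 says "CS patients will undergo PFTs, read the bamboo passage, and complete the LCADL as they did during Research Evaluation 1", and the next sentence brings FEES in as something extra: "Additionally, they will undergo a standardized Fiberoptic Endoscopic Evaluation of Swallowing (FEES".

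**Text pointing to a FEES before training.** The FEES description in the same Research Evaluation 2 section places the exam "in the preoperative clinic or the ARC lab before and after the RST program". The Overview, within its account of Aim 2, says "a FEES will be performed to index baseline swallowing and to provide secondary treatment outcomes". The section on Postoperative Research Evaluation 3 refers back to the FEES protocol of the preoperative exams, in the plural.

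**Analysis.** Aim 3 hypothesises that RST improves postoperative swallowing, among other outcomes. Under Statistical analyses, Aim 3 summarises postoperative swallowing scores descriptively and adds a logistic regression of swallowing safety and efficiency over timepoints that it does not name. Table 9 gives only Exam 3 and 90 days as Aim 3 visits. The comparison with the team's historical data is attached to a list of health-related outcomes. That list is open-ended but does not name the FEES scores.

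**The concern.** A comparison over time can speak to a treatment only if the treatment falls between the measurements, or if something outside shows what would have happened without it. On the visit list, training is finished before the first FEES. Surgery, intubation and early recovery fall between the two FEES exams, and every patient has been trained at both. The regression's time term is then a perioperative change, placed under an aim about the effect of RST.

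These results are meant to inform a larger trial. A rise from Exam 2 to Exam 3 could be read as failure of RST, and a flat result as protection, when neither inference follows. While the schedule contradicts itself, a reader also cannot tell which exams enter the model.

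**Working it through.** The plan states no effect size or power for this analysis, so there is no planned figure to reproduce. The check maps FEES to visits and then asks what each contrast can estimate.

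**Step 1. Contrasts under each reading.**

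| Contrast | Available if | What lies between the exams | What it estimates |
|---|---|---|---|
| Exam 2 vs Exam 3 | either reading | surgery, intubation, recovery | perioperative change in trained patients |
| Exam 1 vs Exam 2 | a pre-RST FEES is done | RST and elapsed time | uncontrolled preoperative change; not in Table 9 |
| Exam 1 vs Exam 3 | a pre-RST FEES is done | RST and surgery | the two mixed |

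None of these isolates an effect of RST on postoperative swallowing.

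**Step 2. The historical aspiration rate.** The Significance section gives 29% aspiration in 182 patients. From the pneumonia row of Table 1, aspirators number 44 + 8 = 52, and 52/182 = 28.6%, which agrees. The reintubation row has 45 in place of 44, giving 53/182 = 29.1%.

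**Step 3. The odds ratio on the planned scale.** OR = [p3/(1 − p3)] / [p2/(1 − p2)], as a marginal odds ratio, where p2 and p3 are the Exam 2 and Exam 3 aspiration rates. The documents give no preoperative rate, so every p2 is assumed. The halving (29% to 14.5%) is also an assumption.

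- RST halves aspiration, p2 = 5%: (0.145/0.855)/(0.05/0.95) = 0.1696/0.0526 = 3.22.
- RST inert (p3 = 29%): OR = 3.22 requires Exam 2 odds of 0.4085/3.222 = 0.1268, so p2 = 0.1268/1.1268 = 11.25%.

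| Assumed Exam 2 rate | OR if RST halves 29% | OR if RST does nothing |
|---|---|---|
| 5% | 3.22 | 7.76 |
| 11.25% | 1.34 | 3.22 |
| 14.5% | 1.00 | 2.41 |
| 20% | 0.68 | 1.63 |
| 25% | 0.51 | 1.23 |

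The odds ratio alone does not separate the two cases. The study will observe p2, and p2 with the odds ratio gives back p3. Judging p3 then needs the postoperative rate in untrained patients, which the contrast does not contain.

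**Step 4. A benefit that cancels.** If RST multiplies the odds by k at both exams, the ratio is (k × o3)/(k × o2) = o3/o2, where o2 and o3 are the odds without RST. With 94% unsafe swallowing postoperatively (Significance) and an assumed 30% before surgery, it is (0.94/0.06)/(0.30/0.70) = 36.6 for k = 1, 0.5 or 0.25.

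**Step 5. What an external comparison could show with n = 25.** Clopper-Pearson 95% limits are the 0.025 quantile of Beta(x, n − x + 1) and the 0.975 quantile of Beta(x + 1, n − x). All 25 patients are assumed to have Exam 3.

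- 2/25 aspirators: 8%, interval 1.0–26.0%, which excludes 29%.
- 3/25: 12%, interval 2.5–31.2%, which does not.
- 20/25 unsafe: 80%, interval 59.3–93.2%, which excludes 94%.
- 21/25: 84%, interval 63.9–95.5%, which does not.
- Historical 52/182: 28.6%, interval 22.1–35.7%.

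The reference is itself uncertain, so this comparison can only be descriptive.

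**The case against.** **Pilot status.** The plan calls itself a proof-of-concept cohort, explains why it has no comparison group, puts description before testing and declines a power-based sample size. That stands, and the lack of a control is not the complaint. Pilot status does not settle which visits include FEES or which enter the model.

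**Descriptive coverage.** Aim 3's stated predictions concern postoperative levels, such as low rates of unsafe swallowing, and those levels will be summarised. The plan nowhere says that the regression estimates an RST effect. Both points are correct. The problem is an unlabelled contrast placed under a hypothesis about RST, which invites that reading.

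**Stronger readings that the documents do not support.**

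- A reader might infer that both FEES certainly follow training, with one stray phrase against it. The conflict is wider than that: the Overview, the FEES description and the Exam 3 section all lean the other way, and the timeline figure is not available here. The Overview also places FEES within Aim 2 as a secondary treatment outcome, so a pre- versus post-RST comparison may have been intended there.
- Working in percentage points, a reader might set 5% to 14.5% (+9.5) beside 20% to 29% (+9.0) and call effective and inert training nearly indistinguishable. On the scale of the planned model these are odds ratios of 3.22 and 1.63. They also rest on different Exam 2 rates, which the study will measure. At any one Exam 2 rate the two cases differ by a factor of 2.41, but using that fact requires the untrained 29% from outside the study.

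**Conclusion.** The concern holds in two parts. First, the FEES schedule is contradictory and must be reconciled; this rests on the text alone. Second, as written, the regression cannot test Aim 3's swallowing hypothesis. If the Research Evaluations list governs, it estimates perioperative change in an uncontrolled, all-trained cohort. If a pre-RST FEES exists, the added contrasts are uncontrolled or mix RST with surgery.

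The size shown is illustrative: an odds ratio of 3.22 fits either a halving of aspiration with a 5% preoperative rate or no effect with an 11.25% rate. It depends on assumed preoperative rates and on the historical 29% applying to these patients. The non-attribution itself does not depend on those figures.

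This should be fixed, but it concerns the interpretation and reporting of Aim 3. A reader might infer that the pilot as a whole is compromised. The documents do not support that: Aim 1 and the listed Aim 2 analyses do not use these FEES contrasts.

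**What to change.** 1. Reconcile the Overview, the Research Evaluations paragraph, the three Research Evaluation sections and Table 9 on which exams include FEES. No added procedure is asked for.
2. Under Statistical analyses, Aim 3, name the timepoints. Label Exam 2 versus Exam 3 as perioperative change and not as evidence of an RST effect. If a pre-RST FEES is already part of the study, list Exam 1 versus Exam 2 in Table 9 as a secondary, uncontrolled contrast; the Overview points to Aim 2 for it.
3. Extend the historical comparison explicitly to Exam 3 aspiration (PAS 6 or more, Table 4) and unsafe swallowing. Give exact 95% intervals beside the 182-patient FEES cohort (29% and 94%). Use that cohort's own definitions, since the Significance section does not define unsafe swallowing by PAS score. Describe the comparison as non-randomised and descriptive.

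The cost is protocol and SAP wording only, with no added patients, visits or procedures; the reference cohort is the team's own. The downside is a weaker claim from Exam 2 versus Exam 3.

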**Table 1. CS patient outcomes stratified by cough response profiles to expel tracheal aspirate.**

[figure not shown]
Outcome: N (%)	CS Aspirators with:		CS Non- Aspirators:	P Value:
	Absent / Ineffective Cough	Effective Cough:		
Pneumonia	10/44 (23%)	0/8 (0%)	11/130 (9%)	0.04*
Reintubation	13/45 (29%)	0/8 (0%)	7/130 (5%)	<0.001*
90-day Mortality	4/44 (9%)	0/8 (0%)	1/130 (1%)	0.04*
30-day Readmission	4/26 (15%)	0/5 (0%)	13/85 (15%)	0.33

Our data, combined with other published reports documenting suboptimal outcomes in aspirating CS patients, highlight the *need for targeted interventions to improve swallowing and airway clearance abilities in CS patients that mitigate the development of associated sequelae and improve patient outcomes*. Unfortunately, no such intervention studies currently exist in the literature, resulting in gaps in knowledge and suboptimal patient care in this area.

While many dysphagia risk factors cannot be modified, **airway physiologic capacity represents one dysphagic risk factor that can be modified (increased) via targeted exercise programs**. Respiratory strength training (RST) has been utilized across several high-risk dysphagia patient populations that is noted to improve physiologic and patient outcomes. First applied in individuals with Parkinson's disease (PD), a 4-week RST was noted to increase cough effectiveness, swallowing safety (penetration-aspiration scale [PAS] scores), and hyolaryngeal excursion during swallowing. Likewise, a 4-5 week RST program implemented in stroke survivors was reported to improve maximum expiratory pressure (MEP), cough peak expiratory flow, cough volume acceleration, reflexive urge to cough responses, and swallowing safety. Similarly, in HNC patients with chronic radiation associated dysphagia, implementation of an 8-week RST program led to improved expiratory pressure generating capacity, swallowing safety, and patient reported quality of life.

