**Pulmonary function testing (PFT):** Consistent with PFT protocols and the American Thoracic Society guidelines, all PFT measures will be completed in an upright seated position with a nose clip. FVC will be measured with a handheld spirometer (Micro I; Carefusion, Yorba Linda, California). For FVC, CS patients will be instructed to take a deep breath in, place their mouth around the mouthpiece, and blow all the air out from their lungs. MEP and MIP will be measured with the MicroRPM handheld MEP device (Micro Direct Inc., Lewiston, ME). For MEP testing, CS patients will be instructed to place their mouth around the mouthpiece and blow out as forcefully as possible. For MIP testing, CS patients will be instructed to place their mouths around the mouthpiece and breathe in as forcefully as possible. The participant will perform up to three trials of each task, inter-spaced with a one-minute rest in between. The highest value will be used for statistical analysis. Voluntary cough PEF will be tested using a handheld analog Mini-Wright Peak Cough Flow Meter (model number 3103085, Clement Clarke Int., Harlow, United Kingdom). This device is considered the gold standard Peak Cough Flow (PCF) device and is one of the only PCF devices that contains a one-way expiratory valve that prevents a participant to breathe air in from the device to reduce contamination. Additionally, we will fit the PCF meter with a Mini-Wright disposable single-use bacterial expiratory one-way valve filter mouthpiece (model number 3122064) that traps any expectorated matter or organisms ensuring a barrier to the PCF meter device. This method conforms to the American Thoracic Society (ATS) standards for PCF testing. Participants will be instructed to "cough hard like something is stuck in your throat." The participant will perform three trials inter-spaced with a one-minute rest in between. The outcome will be **Peak Expiratory Flow** ((PEF) L/min). The highest obtained value will be used. For cough spirometry testing, an oral pneumotachograph (MLT 1000; ADInstruments, Inc., Colorado Springs, Colorado) will be connected to a spirometry mouthpiece filter (MQ 304 Spirometer Filter; Vacumed; Ventura, California). Participants will be instructed to wrap their lips around the mouthpiece and "cough hard like something is stuck in your throat." Cough waveforms will be recorded using LabChart Version 7 (Microsoft Corp., Redmond, Washington) and a laptop computer devoted to this study. Cough spirometry metrics will include inspiratory phase duration, inspiratory peak flow rate, compression phase duration, expiratory rise time, peak expiratory flow rate, and cough volume acceleration. Up to three attempts will be elicited. An example of voluntary cough spirometry waveform from a previous study in our lab is provided in Fig. 5 and definitions for each outcome of interest is provided in Table 3 below.

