
**Table 3. Definitions of cough spirometry outcomes of interest**

Cough Outcome:	Definition:
Inspiratory phase duration (s)	Time from onset of inspiration at 0L/s to the beginning of glottic closure or the start of the expiration onset
Inspiratory peak flow rate (L)	Peak inspiratory flow during the inspiratory phase
Compression phase duration (s)	Time to glottic opening; end of the inspiratory phase to the start of the expiratory phase
Expiratory rise time (s)	Time from the expiration phase to the peak of the expiratory flow
Peak expiratory flow rate (L)	Peak expiratory airflow during the expiratory phase of cough
Cough volume acceleration (L/s/s)	Peak expiratory flow rate /expiratory rise time

Note: L=liters, s=seconds

**Functional Dyspnea Measure:** Research participants will complete the London Chest Activity of Daily Living scale (LCADL), which is a standardized and validated 15-item questionnaire that measures dyspnea during activities of daily living.

**Speech Measure:** The 'Bamboo Passage' is a validated speech testing item that consists of a 98-word paragraph. It is used to determine speaking rate, and number and duration of pauses during speech. Participants will be instructed to read the passage in their normal speaking rate and loudness. Speaking rate (words per minute), number of pauses, and duration of pauses will be calculated.

A digital audio recorder (TASCAM, DR40) connected to a condenser headset microphone (AKG, Inc., HSC271) with a lapel windscreens (eBoot, Inc.) will be placed on the participants head with the headset microphone at a standardized distance of 10cm from the right lip corner. Audio recordings will be digitized at 44.1 kHz with a 16-bit quantization. Calibration of the microphone will be completed prior to each test. Speech testing items will be recorded and saved for subsequent offline analysis. Audio recordings obtained during speech testing will be blinded and rated in Audacity (Audacity 2.2.2, WordPress, 2018) for the below speech outcomes.

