**Aim 2 Outcomes:** Given our desire to index physiologic capacity, we will utilize the highest obtained outcome for FVC, MEP, MIP, cough PEF, and cough spirometry metrics at each time point before and after RST for statistical comparisons. LCADL ratings and speech measurements will also be compared before and after RST. We hypothesize that CS patients will improve FVC, MEP, MIP, cough PEF, cough spirometry metrics, dyspnea, and speaking rate/pauses post-RST.

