**Sample size justification:** Given that this is a pilot study to determine primarily safety and feasibility data to determine whether a large-scale clinical trial is warranted, a justification based on statistical power to test hypotheses strictly at the  $\alpha=0.05$  level is not appropriate. The findings from this exploratory study will be used to perform future sample size and power calculations to examine the safety, feasibility, and impact of preoperative RST in a larger cohort of CS patients.

**Statistical analyses:** Descriptive statistics, magnitudes of estimates, and spaghetti and needle plots that visualize individual-level data across time points will first be utilized to summarize data in this small cohort and prior to performing conventional analyses and hypothesis testing.

**Aim 1:** Attendance, RST adherence, and adverse events will be summarized descriptively with frequency counts and percentages.

**Aim 2:** Descriptive statistics and an appropriate repeated measures analysis based on the distribution of data will be used to evaluate potential change in FVC, MEP, MIP, voluntary cough peak expiratory flow, and cough spirometry metrics, speech rate, number of pauses, duration of pauses, LCADL ratings across time points (pre-RST vs. post-RST).

**Aim 3:** Descriptive statistics will be used to summarize swallowing safety profiles postoperatively (frequency histogram, mean, mode, range of PAS, DIGEST, NZSS, YRS scores), and logistic regression will be used to compare swallowing safety and efficiency across timepoints. Postoperative rates of pneumonia, reintubation, duration of intubation, intubation fast track status, any related respiratory therapy outcomes, 30-day readmission, mortality, and time to oral intake/hospital LOS, etc. will be summarized descriptively (frequency counts, %) and compared to our historical data set in CS patients.

**Data Management and Quality Control:** Research Electronic Data Capture (REDCap) will be used to enter and store data for the current study, which is a secure web-based application hosted at the University of Florida. REDCap has a variety of features that streamline data entry and processing including the ability to download and export data directly to commonly used statistical analyses software. The ARC lab has successfully used REDCap for data collection, storage, and analyses for other research studies

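### Taken literally, the highest-value rule for Aim 2 picks the slowest expiratory rise time, and no favourable direction is stated for the other two cough durations

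*Combined protocol and SAP*

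**What the plan says.** Aim 2 Outcomes gives the purpose as indexing physiologic capacity and then sets the rule: "we will utilize the highest obtained outcome for FVC, MEP, MIP, cough PEF, and cough spirometry metrics at each time point". The hypothesis in the same paragraph is also collective: "We hypothesize that CS patients will improve FVC, MEP, MIP, cough PEF, cough spirometry metrics".

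The pulmonary function testing text under Research Evaluation 1 names six cough spirometry metrics: inspiratory phase duration, inspiratory peak flow rate, compression phase duration, expiratory rise time, peak expiratory flow rate and cough volume acceleration. It has its own selection sentence for FVC, MEP and MIP ("The highest value will be used for statistical analysis") and another for the handheld cough flow meter ("The highest obtained value will be used"). For cough spirometry it says only "Up to three attempts will be elicited".

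Table 3 defines cough volume acceleration as "Peak expiratory flow rate /expiratory rise time". The Significance section, describing a programme in stroke survivors, says that it "was reported to improve maximum expiratory pressure (MEP), cough peak expiratory flow, cough volume acceleration". The Aim 2 paragraph of the statistical analyses says that "an appropriate repeated measures analysis based on the distribution of data will be used to evaluate potential change". Neither that paragraph nor Table 9 adds a selection rule or a direction for any single metric.

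**The concern.** Taking the highest of several attempts indexes capacity when more is better, as with a volume, a pressure or a flow. The rule extends this to three durations, where it takes the longest. For rise time the protocol's own definition of acceleration makes the longest value the less favourable one at a given flow. For the other two durations the reader cannot tell whether the longest value is the best, the worst or neither.

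Two things are at stake. A rise time reported under the literal rule would not describe the patient's capacity. And a change in inspiratory phase or compression phase duration, in either direction, could be called an improvement once the data are known.

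**Working it through.** **1. Which rule governs.** The plan states no figure to reproduce here, so the first check is of the text. The two selection sentences in the pulmonary function testing text follow the FVC/MEP/MIP trials and the flow meter trials. Neither covers cough spirometry. The sentence in Aim 2 Outcomes is therefore the only selection rule for the six metrics, and it has no exception.

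**2. Does the highest value fit the purpose?**

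| Metric | Highest value means | Fits indexing of capacity? |
|---|---|---|
| Inspiratory peak flow rate | strongest flow | yes |
| Peak expiratory flow rate | strongest flow | yes |
| Cough volume acceleration | fastest acceleration | yes |
| Expiratory rise time | slowest rise | no, at a given flow |
| Inspiratory phase duration | longest phase | no direction stated |
| Compression phase duration | longest phase | no direction stated |

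**3. Rise time.** With A the acceleration, F the peak expiratory flow and T the rise time, Table 3 gives A = F/T. At fixed F, A falls as T rises. With invented values, F = 5 L/s and T = 0.04, 0.06, 0.10 s:

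- 5/0.04 = 125 L/s/s
- 5/0.06 = 83.3 L/s/s
- 5/0.10 = 50 L/s/s

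The rule records 0.10 s for rise time but 125 L/s/s for acceleration: the slowest cough for one metric and the fastest for the other. The unfavourable direction is derived from Table 3 together with the Significance text. The protocol does not state it outright.

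**4. Size of the ambiguity.** The documents give no cough-to-cough variability, so every input here is assumed: mean rise time 60 ms, lognormal, log-SD 0.30 (range 0.10 to 0.45), three coughs, flow CV 15%, flow and rise time uncorrelated (range -0.6 to +0.6).

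- Highest of three averages 76 ms (65 to 84); lowest of three averages 46 ms (55 to 39). The two readings differ by about 30 ms (10 to 45).
- The slowest cough is also the lowest-acceleration cough in 79% of visits (37% to 90%).

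**5. Effect on the pre/post comparison.** With the same number of attempts and the same spread at both exams, the shift from taking an extreme is the same at both, and the pre/post ratio is unbiased. If the mean is unchanged but log-SD falls by one third, the highest of three gives a ratio of 0.93 (0.97 to 0.90) and the lowest of three about 1.10 (1.03 to 1.16). Nothing in the documents says that such a fall will occur.

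**6. Do separately selected values fit Table 3?** Not necessarily, under either rule. Invented coughs with flows 5.0, 4.5, 4.0 L/s and rise times 0.05, 0.06, 0.10 s have accelerations 100, 75, 40. The literal rule records 5.0, 0.10 and 100, although 5.0/0.10 = 50. Taking the shortest rise time instead records 5.0, 0.05 and 100, which agree. But two coughs with flows 5.0 and 4.5 and rise times 0.06 and 0.05 have accelerations 83.3 and 90. The shortest-time rule then records 5.0, 0.05 and 90, although 5.0/0.05 = 100.

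**The case against.** The best defence is that the sentence opens with its purpose, so for a list that mixes volumes, pressures, flows and times the highest value naturally means the best performance. On that reading the wrong direction for rise time disappears. This is plausible, but the text does not say it, and it does not help the other two durations, because best is undefined without a direction. A convention might lie in the reference cited for Table 3 or in the example waveform figure, neither of which is available here; nothing shows that either supplies one.

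A second defence is that little depends on this. The planned analysis looks for change, and a repeated measures comparison of two time points is the same test whichever direction is called favourable. That stands. It limits the harm to the reported level of rise time and to the interpretation of the durations.

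Three stronger readings are tempting, and the documents do not support them:

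- *That the rule biases the pre/post comparison.* It does not when attempts and spread are equal. The ratio of 0.93 needs an assumed fall in spread.
- *That mixing coughs is an error in itself.* No planned analysis divides reported flow by reported rise time or requires all metrics to come from one cough.
- *That the protocol treats acceleration as improved by training in general.* The sentence in Significance concerns stroke survivors. It supports the favourable direction of acceleration and no more.

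**Conclusion.** The concern holds for three of the six cough spirometry metrics. Rise time has a written rule that, followed literally, selects the value opposed to its stated purpose. Inspiratory phase and compression phase duration have a selection rule and a hypothesis of improvement without a direction that would give either a meaning.

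The harm is minor. The study is a 25-patient pilot run primarily for safety and feasibility, and the plan declines a justification based on power. Aim 1, FVC, MEP, MIP, meter-based cough PEF, the two spirometry peak flows and acceleration are untouched. A reader might infer that Aim 2 as a whole is compromised; it is not.

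The direction for rise time rests only on the Table 3 formula at a given flow and on acceleration being counted as a gain. The millisecond figures are illustrations on assumed inputs, and the conclusion does not depend on them.

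**What to change.** In Aim 2 Outcomes:

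- Keep the highest value for FVC, MEP, MIP, cough PEF, inspiratory peak flow rate, peak expiratory flow rate and cough volume acceleration.
- Use the shortest obtained value for expiratory rise time.
- For inspiratory phase and compression phase duration, state a selection rule and a direction before data are seen. Otherwise report their change descriptively and take them out of the hypothesis of improvement.

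The cost is two or three sentences. The waveforms are already recorded, so no further testing is needed. Two limitations remain. The shortest of three is still sensitive to a change in cough consistency (ratio about 1.10 for the assumed one-third fall in log-SD from 0.30). And the separate metrics may come from different coughs, so reported flow, rise time and acceleration need not satisfy Table 3 jointly.

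An optional alternative is to take all six metrics from the cough with the highest peak expiratory flow rate. The values then agree with Table 3, but a metric that had no defect is weakened. Under the same assumed inputs that cough is not the highest-acceleration cough in about 49% of visits, and acceleration is about 12% lower and noisier (log-SD 0.32 against 0.25). A direction for each duration would still have to be stated.

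Because the plan allows up to three attempts, it would also help to analyse the same number per patient at both exams, since the absence of pre/post bias depends on that.
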